8 TREATMENTS

8.1 Details of Study Product

Prontosan Wound Irrigation Solution is a clear, colorless liquid containing purified water, 0.1% undecylenamidopropyl betaine as a surfactant, 0.1% polyaminopropyl biguanide (polyhexanide [PHMB]) as a preservative, and sodium hydroxide for pH adjustment. The device is cleared by the FDA for prescription and over-the-counter use for cleaning wounds and for moistening and lubricating absorbent wound dressings for the management of cuts, lacerations, ulcers, burns, post-surgical wounds, and abrasions.^{7,8}

Prontosan Wound Gel is a clear, colorless gel containing glycerol, hydroxyethylcellulose, 0.1% undecylenamidopropyl betaine, 0.1% PHMB, and purified water. The device is cleared by the FDA for prescription and over-the-counter use for cleaning and moistening the wound bed and for the management of cuts, abrasions, lacerations, ulcers, first- and second-degree burns, partial and full thickness wounds, and surgical incisions. It can be used during wound dressing changes to soften encrusted wound dressings.^{18,19}

Commercially available Prontosan solution and commercially available Prontosan gel will be provided by the Sponsor for the study. Prontosan solution will be provided in 350-mL bottles and packed in cartons containing up to 10 bottles. Prontosan gel will be provided in 30-mL bottles and packed in cartons containing up to 20 bottles. Each carton will be labeled with the name and address of the Sponsor, the lot number, the expiration date, and will contain the product usage instructions. Cartons will be distributed to the study sites.

Storage

Prontosan solution and Prontosan gel are to be stored under controlled room temperature. Controlled room temperature is defined by the United States Pharmacopeia (USP) as 20 to 25°C (68 to 77°F) with allowed excursions between 15 to 30°C (59 to 86°F). Avoid storing these products in excessive heat, and do not refrigerate or freeze these products.

Use Prontosan solution and Prontosan gel prior to the expiration dates noted on the package labels. Prior to opening the bottle, the product is sterile by aseptic filtration (<1 CRU/mL), and the fluid and fluid path is nonpyrogenic prior to removal of the cap.

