11.4 Adverse Events

11.4.1 Adverse Events

An AE is any symptom, physical sign, syndrome, or disease that either emerges during the study or, if present at screening, worsens during the study, regardless of the suspected cause of the event. All medical and psychiatric conditions (except those related to the indication under study) present at screening will be documented in the medical history eCRF. Changes in these conditions and new symptoms, physical signs, syndromes, or diseases should be noted on the AE eCRF during the rest of the study. Clinically significant laboratory abnormalities should also be recorded as AEs.

Adverse device effects (ADEs) are defined as AEs that are considered related to the study device. Possible anticipated ADEs with Prontosan solution or Prontosan gel include burning sensation, itching, and rash. In rare cases (1:10,000), anaphylactic shock has been reported after use of Prontosan solution or Prontosan gel.^{9,10}

Patients and/or caregivers will be instructed to report AEs in the diary, and patients will be monitored for AEs at each study visit. All AEs are to be followed until resolution or until a stable clinical endpoint is reached.

Each AE is to be documented in the eCRF with reference to start and stop dates, frequency, severity, relationship to study device (related: yes or no), action taken with study device, treatment of event, and outcome. Furthermore, each AE and each ADE are to be classified as being serious or non-serious. Changes in AEs and AE resolution dates are to be documented in the eCRF.

For the purposes of this study, the period of observation for collection of AEs extends from the time the patient gives informed consent until the final visit. Follow-up of an AE, even

after the end of treatment, is required until the event resolves or stabilizes at a level acceptable to the Investigator.

Specific guidelines for classifying AEs by intensity are given in Table 3.

Table 3 Classification of Adverse Events by Intensity

Mild: An event that is easily tolerated by the patient, causing minimal discomfort and not interfering with everyday activities.
Moderate: An event that is sufficiently discomforting to interfere with normal everyday activities.
Severe: An event that prevents normal everyday activities.

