12 STATISTICAL ANALYSIS

A Statistical Analysis Plan (SAP) will be prepared after the protocol and eCRF are approved. This document will provide further details regarding the definition of analysis variables and analysis methodology to address all study objectives. The SAP will serve as a complement to the protocol and supersedes it in the case of any differences.

The statistical evaluation will be performed using the Statistical Analysis Software (SAS®) Version 9.2 or higher (SAS Institute, Cary, NC). All data will be summarized using descriptive statistics, and where necessary, data will also be listed. For continuous variables, data will be summarized with the number of patients (N), mean, standard deviation (SD), median, minimum, and maximum. For categorical variables, data will be tabulated with the number and proportion of patients for each category.

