12.6 Safety Analysis

All reported AEs will be coded using the Medical Dictionary for Regulatory Activities. The incidence of TEAEs (events with onset dates on or after the start of the study treatment) will be included in incidence tables. Events with missing onset dates will be included as treatment-emergent. If a patient experiences more than 1 occurrence of the same AE, the occurrence with the greatest severity and the closest association with the study device will be used in the summary tables. SAEs, AEs causing discontinuation, and ADEs will be tabulated. All AEs will be listed by patient, along with information regarding onset,

duration, severity, relationship to study device, action taken with study device, treatment of event, and outcome.

Clinical laboratory data, vital signs, physical examination results, wound history, and medical history will be listed by patient.

Listings and summary tables will be provided for prior medications and for concomitant medications initiated or continued during the study period. Study treatment exposure will be listed by patient and summarized descriptively.

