5.2.6 Adverse Events

Any adverse event that occurs at or after first study treatment administration and up to the end of the study treatment is considered as treatment emergent adverse event (TEAE).

An adverse event starting before the first study treatment and worsened in intensity between the first administration of study treatment and the end of the study treatment will also qualify as a treatment emergent adverse event (TEAE).

Pre-existing diseases or conditions occurring before screening visit are considered to be medical history and should be recorded as TEAEs only if they worsen (untoward change in intensity, frequency, or quality) after the first study treatment.

For adverse events where the intensity changes over time, the maximum intensity observed during the whole duration of the adverse event will be documented and captured in the database. If the adverse event stopped and reoccurred with a different or the same intensity, it will be entered as new adverse event in the eCRF.

All AEs with start date after screening visit but before first study treatment administration and that do not worsen after the first study treatment administration, and all AEs with start date after the date of end study treatment will be regarded as non-TEAE. This study will not display non-TEAEs in the tables or listings.

In case of incomplete start/stop date, an AE will be considered as non-TEAE if this can be concluded without any doubt. All other cases will be considered TEAE occurred during the 4-week treatment period. The non-TEAEs will not be included in the AE analysis.

Related TEAEs are entered “yes” as documented in the eCRF.

The following overview table will be generated.

Summary of the number of patients with

- At least 1 TEAE
- At least 1 serious TEAE
- At least 1 related TEAE
- At least 1 TEAE leading to discontinuation from the treatment (i.e. TEAE with “Action take with Prontosan due to AE”: “stopped both”)
- A TEAE with a fatal outcome

Unless stated otherwise, the following TEAE summaries will be presented:

The number and percentage of patients with serious TEAEs will be summarized by System Organ Class (SOC) and PT (sorted alphabetically).

The percentage denominator will be the number of patients in the safety population.

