Adverse Device Effects (ADEs) are considered as AEs that are related to the study device. The possible anticipated ADEs with Prontosan solution or Prontosan gel include AEs: burning sensation, itching, and rash. The suspected unexpected serious adverse reactions (SUSARs) are

serious ADEs that have not previously been documented in the protocol or other safety information.

The number and percentage of patients with ADEs will be summarized by SOC and PT (sorted alphabetically) for each

- ADE
- Serious ADE

Only serious AEs and ADEs will be coded according to MedDRA, version 20.0 or higher. All AEs will be listed. All AE analysis will be conducted in the safety population.

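### The only AE-discontinuation row in SAP 5.2.6 requires both products to be stopped, so it omits a patient who stops just the solution or just the gel because of a TEAE

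*SAP*

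**What the plan says.** SAP 5.2.6 lists five rows for the TEAE overview. One is "At least 1 TEAE leading to discontinuation from the treatment", with a definition in brackets: "i.e. TEAE with “Action take with Prontosan due to AE”: “stopped both". The bracket is introduced as a definition, not as an example. The denominator for the AE summaries is the safety population, which SAP 4.3 defines as everyone with at least one administration.

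The treatment is two separate products. Protocol 8.1 states: "Commercially available Prontosan solution and commercially available Prontosan gel will be provided by the Sponsor for the study". Protocol 8.2 uses them in sequence, the solution to clean and then the gel as a coating. For each AE the eCRF records, among other items, "action taken with study device, treatment of event, and outcome" (Protocol 11.4.1).

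Protocol 12.6 commits to a tabulation with no condition about both products: "SAEs, AEs causing discontinuation, and ADEs will be tabulated". Protocol 12 says that the SAP "supersedes it in the case of any differences", so the SAP definition governs. SAP 5.2.6 also says "All AEs will be listed".

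**The concern.** Every objective in Protocol 5.1 and SAP 2 concerns treatment with the solution and the gel together. A patient who drops one of them because of a reaction is no longer on the regimen under study, yet adds nothing to the only count of AE-driven stopping. The SAP itself says: "The possible anticipated ADEs with Prontosan solution or Prontosan gel include AEs: burning sensation, itching, and rash". These are reactions to what is applied to the wound, so whether a product was stopped because of them is what a reader of a post-marketing device report would look for in that row.

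Specifying both products has little purpose unless the form can also record something less than both. If it can, the plan collects that information and then leaves it out of the summary tables.

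**Working it through.** The plan gives no figure for AE-related stopping, so there is none to reproduce on this point. The check is a comparison of texts, followed by simple bounds.

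**Step 1: where could a single-product stop be counted?**

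| Place | Captures a TEAE that led to stopping one product? |
|---|---|
| SAP 5.2.6, discontinuation row (Table 11.1) | No, both products are required |
| SAP 5.2.6, any-TEAE row | Patient counted, but not as a stop |
| SAP 5.2.6, related-TEAE row; ADE Tables 11.2 and 12.1 | Patient counted if the event is related, but not as a stop |
| SAP 5.1.8 and Table 5.1, weekly exposure | Shows product use, without a link to an AE |
| Listings 10.1 and 10.2 | Event listed (10.2 if related); Protocol 12.6 includes the action taken in the AE listing |

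No other row in SAP 5.2.6 and no title in the SAP 6 table list gives a count of such stops.

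**Step 2: direction.** Let B be the number of patients with a TEAE coded as both products stopped, S the number of other patients who stopped a product because of a TEAE, and N the safety population.

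- The SAP row shows B/N.
- A row for any product stopped would show (B + S)/N.
- The difference is S/N, which cannot be negative.

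**Step 3: size.** S is not given anywhere, so these are assumptions shown as a range. Take N = 52, the planned number of patients to complete the study.

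| B | S | SAP row | Any product stopped |
|---|---|---|---|
| 0 | 1 | 0/52 = 0.0% | 1/52 = 1.9% |
| 0 | 2 | 0/52 = 0.0% | 2/52 = 3.8% |
| 1 | 1 | 1/52 = 1.9% | 2/52 = 3.8% |
| 1 | 3 | 1/52 = 1.9% | 4/52 = 7.7% |
| 1 | 4 | 1/52 = 1.9% | 5/52 = 9.6% |

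The safety population includes early withdrawals who are later replaced, so N may exceed 52. At an assumed N of 60, each patient is 1/60 = 1.7 points. If the target of 52 is met, 1.9 points per patient is a ceiling.

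**Step 4: chance that the gap arises.** If the true rate of single-product stops for a TEAE is p, the chance of at least one in 52 patients is 1 − (1 − p)^52, and the expected number is 52p.

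| Assumed p | Chance of at least one | Expected number |
|---|---|---|
| 1% | 41% | 0.5 |
| 2% | 65% | 1.0 |
| 5% | 93% | 2.6 |
| 10% | 99.6% | 5.2 |

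**Step 5: sequential stops.** The definition works on one event at a time. If the gel is stopped for one TEAE and the solution later for another, it is possible that neither event carries the both-products code, although the patient has stopped the whole regimen. This depends on how the form is completed, and the SAP has no rule for it.

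**The case against.** The definition is coherent. The regimen is solution plus gel, and discontinuing the treatment can reasonably mean that all of it has ended; the SAP states its coding openly. This stands: the row is not an error for whole-regimen discontinuation.

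A reader might infer that the SAP breaks the protocol's commitment in 12.6. The documents do not establish that. Protocol 12.6 leaves the term undefined, and the safety follow-up text in Protocol 6.1 and the withdrawal text in 7.4 use discontinuation for a patient leaving treatment or the study. A patient who drops one product and stays in the study may fall outside the commitment.

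A reader might also infer that the tolerability summary as a whole is biased, or that stopping one product alone is the likely response to a local reaction. Neither is supported. The any-TEAE, related-TEAE and ADE counts are untouched, and the listings carry the events. The documents attribute the same reactions to either product, and both contain 0.1% PHMB and 0.1% undecylenamidopropyl betaine. Nothing says how often one would be stopped alone.

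Finally, the eCRF is not among the documents, so its single-product options are inferred from the wording of one code. Safety is also not a stated objective of this single-arm study. These points limit the severity. They do not remove the gap in the one row.

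**Conclusion.** The point holds as a low-severity reporting gap. The discontinuation row in Table 11.1 is a valid count of patients with a TEAE coded as both products stopped. Read as a measure of AE-driven stopping of the regimen under study, it can only understate, because patients who stop one product are left out and none can be wrongly added by that rule.

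The size cannot be stated. It is at most about 1.9 percentage points per such patient, provided that the safety population reaches 52; with fewer patients, each would weigh more. The scenarios with several single-product stops are illustrations, not forecasts. The conclusion rests on the form being able to record a stop of one product. The sample size, the paired t-test and all Wound-QoL analyses are unaffected.

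**What to change.** In SAP 5.2.6 and Table 11.1:

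- Keep the existing row and label it as TEAE with both products stopped.
- Add a row for TEAE leading to stopping any Prontosan product, with sub-rows for solution only, gel only and both.
- Derive these per patient across all of that patient's TEAEs, so that stopping one product for one event and the other for a later event counts as both.
- Use the action-taken field of the AE form, if it has single-product options. If it does not, one sentence in the SAP saying so closes the point.

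The cost is a few table rows and one derivation rule; no new data are collected if the options exist. The change concerns reporting only and says nothing about when a product should be stopped.

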5.2.7 Analysis of Other Assessments

5.2.7.1 Vital Signs

Vital signs will be measured at Week 0 screening visit and Week 5/or early discontinuation visit. Vital signs comprise systolic and diastolic blood pressure, pulse rate and temperature.

Vital signs parameters will be listed for the safety population.

5.2.7.2 Laboratory Parameters

Laboratory parameters are assessed at screening visit and Week 5/or early discontinuation visit. Only clinically significant laboratory parameters will be recorded. All available laboratory data will be listed for the safety population. This data will also be summarized using the safety population.

5.2.7.3 Physical Examination

A complete physical examination (head, ears, eyes, nose, throat, heart, lungs, abdomen, skin, cervical and axillary lymph nodes, neurological, and musculoskeletal systems) will be performed at the screening visit. A brief physical examination will be performed at the Week 5 visit (end of treatment or early discontinuation).

Physical examination data in terms of whether the examination was performed or not including the reason will be listed for the safety population.

5.2.8 Interim Analysis

No interim analysis is planned in the study.

6. TABLES, LISTINGS, AND FIGURES

Table of Contents for OPM-G-H-1506

Tables

	1. Subject disposition
Table 1	Overall patient disposition including reasons for exclusion from analysis populations– Enrolled population
	2. Protocol deviations
Table 2	Protocol deviations – Safety Population and Evaluable Population
	3. Demographic and baseline characteristics
Table 3	Demographic and baseline characteristics – Safety Population and Evaluable Population
	4. Wound history
Table 4	Wound History – Safety Population and Evaluable Population
	5. Study medication exposure and compliance
Table 5.1	Treatment and exposure to study product under this protocol – Safety Population
Table 5.2	Treatment and exposure to study product under this protocol – Evaluable Population
	6. Efficacy – Wound-QoL questionnaire scores
Table 6.1	Wound-QoL global scores and changes from baseline by week – descriptive statistics and paired t-test for week 5 – Evaluable Population
Table 6.2	Wound-QoL Body subscores and change from baseline by week – descriptive statistics – Evaluable Population
Table 6.3	Wound-QoL Psyche subscores and change from baseline by week – descriptive statistics – Evaluable Population
Table 6.4	Wound-QoL Everyday Life subscores and change from baseline by week – descriptive statistics – Evaluable Population
Table 6.5	Wound-QoL global scores and changes from baseline by week – descriptive statistics and paired t-test for week 5 – Safety Population
Table 6.6	Wound-QoL Body subscores and change from baseline by week – descriptive statistics – Safety Population
Table 6.7	Wound-QoL Psyche subscores and change from baseline by week – descriptive statistics – Safety Population
Table 6.8	Wound-QoL Everyday Life subscores and change from baseline by week – descriptive statistics – Safety Population
Table 6.9	Wound-QoL global scores and changes from baseline by week – descriptive statistics and paired t-test for week 5 – Completer Population

Table 6.10	Wound-QoL Body subscores and change from baseline by week – descriptive statistics – Completer Population
Table 6.11	Wound-QoL Psyche subscores and change from baseline by week – descriptive statistics – Completer Population
Table 6.12	Wound-QoL Everyday Life subscores and change from baseline by week – descriptive statistics – Completer Population
	7. Efficacy - Wound assessment
Table 7.1	Wound assessment– descriptive statistics – Evaluable Population
Table 7.2	Wound assessment– descriptive statistics – Completer Population
	8. Efficacy - Wound measurement
Table 8.1	Wound measurement – descriptive statistics – Evaluable Population
Table 8.2	Wound measurement – descriptive statistics – Completer Population
	9. Efficacy –Exploratory
Table 9.1	Surrounding erythrema – change from baseline to week 5 - Evaluable Population
Table 9.2	Swelling – change from baseline to week 5 - Evaluable Population
	10. Efficacy –Other exploratory
Table 10.1	Proportion of patients with no score of 3 or 4 given in any individual item of the Wound-QoL questionnaire – Evaluable Population
Table 10.2	Proportion of patients with no score of 3 or 4 given in any individual item of the Wound-QoL questionnaire – Completer Population
	11. Display of adverse events
Table 11.1	Overview of the number of subjects with TEAEs – Safety Population
Table 11.2	Overview of the number of subjects with ADEs – Safety Population
	12. AEs by SOC and PT
Table 12.1	ADEs by primary SOC and PT – Safety Population
Table 12.2	Serious TEAEs by primary SOC and PT – Safety Population
Table 12.3	Serious ADEs by primary SOC and PT – Safety Population
	13. Laboratory value
Table 13	Laboratory samples – descriptive statistics – Safety Population

Listings

	1. Subject disposition
Listing 1.1	Subject completion/discontinuation – Enrolled Population
Listing 1.2	Subject allocation to study population – Enrolled Population
	2. Protocol deviations
Listing 2	Protocol deviations – Enrolled Population
	3. Subjects excluded from analysis
Listing 3	Violation of in-/exclusion criteria – Enrolled Population
	4. Demographic data and baseline background characteristics
Listing 4	Demographic and baseline background data – Enrolled Population
	5. Medical history
Listing 5	Prior and concomitant illnesses – Safety Population
	6. Wound history
Listing 6	Wound history - Safety Population
	7. Prior and concomitant medications
Listing 7	Prior and concomitant medications – Safety Population
	8. Study medication exposure
Listing 8	Exposure – Safety Population
	9. Wound assessment
Listing 9.1	Wound assessment - Safety Population
Listing 9.2	Wound measurement - Safety Population
	10. Adverse event
Listing 10.1	Adverse events – Safety Population
Listing 10.2	Adverse device effects – Safety Population
	11. Laboratory data
Listing11	Laboratory values – Safety Population
	12. Vital signs
Listing 12	Vital signs values – Safety Population
	13. Physical examination
Listing 13	Physical examination – Safety Population

8. APPENDICES

Appendix 1: Wound-QoL Questionnaire

The Wound-QoL questionnaire (shown below) measures the health-related QoL of patients with chronic wounds.^{7,8}

Data Analysis Instructions⁹

If more than one box is ticked within an item or if a patient has ticked between two checkboxes, the item is treated as missing.

Answers to each item are coded with numbers (0='not at all' to 4='very much').

A Wound-QoL global score on overall disease-specific quality of life is computed by averaging all items. A global score can only be computed if at least 75% of the items have been answered (i.e., at least 13 in 17 items are valid).

In addition, subscales of the Wound-QoL can be calculated representing different dimensions of disease-specific quality of life by averaging the respective items. A subscale can only be computed if no more than 1 item of the subscale is missing. The items are assigned to subscales as follows:

1. Subscale 'Body': Items #1 to #5
2. Subscale 'Psyche': Items #6 to #10
3. Subscale 'Everyday life': Items #11 to #16

Item #17 does not belong to either of the subscales.

The following questions are designed to find out how your chronic wound(s) affect(s) your quality of life.

Please check one box per line!

In the last seven days ...		not at all	a little	moderately	quite a lot	very much
1	...my wound hurt					
2	...my wound had a bad smell					
3	...the discharge from the wound has upset me					
4	...the wound has affected my sleep					
5	...the treatment of the wound has been a burden to me					
6	...the wound has made me unhappy					
7	...I have felt frustrated because the wound is taking so long to heal					
8	...I have worried about my wound					
9	...I have been afraid of the wound getting worse or of getting new wounds					
10	...I have been afraid of hitting the wound against something					
11	...I have had trouble moving around because of the wound					
12	...climbing stairs has been difficult because of the wound					
13	...I have had trouble with everyday activities because of the wound					
14	...the wound has limited my recreational activities					
15	...the wound has forced me to limit my contact with other people					
16	...I have felt dependent on help from others because of the wound					
17	...the wound has been a financial burden to me					

